9.3. Database Management and Quality Control	21
10. Data Analysis.....	21
10.1. Statistical Plan	21
10.2. Sample Size Justification	21
10.3. Primary Analysis	22
10.3.1. Procedure Time	22
10.3.2. Number of adverse events	22
10.3.3. Procedure Time	22
10.4. Secondary Analysis	22
10.4.1. Paresthesia coverage	22
10.5. Additional Analysis.....	23
10.6. Data Sets.....	23
11. Withdrawal of Patients from Study	23
12. Modification of Protocol.....	24
13. Discontinuation of Study	24
14. References.....	25
15. Appendix A: Case Report Form Matrix.....	26
16. Appendix B: Patient Questionnaires.....	27

Confidentiality Statement

The confidential information in the following document is provided to you as an Investigator, potential Investigator, or Consultant for review by you, your staff and an appropriate Institutional Review Board or Independent Ethics Committee. By accepting the document you agree that the information contained herein will not be disclosed to others without written authorization from Coordinating Investigator or from St. Jude Medical, except to the extent necessary to obtain informed consent from those persons to whom the products may be administered.

Protocol Summary

Title:	NAPS (Non-Awake versus Awake Placement of Spinal cord stimulators) Study for the evaluation of awake and non-awake methods of SCS paddle lead placement
Study Devices:	Eon Mini™ or Eon™ neurostimulation system with the Penta™ paddle leads or the Lamitrode C-series™ paddle leads.
Objectives:	Determine whether non-awake placement of spinal cord stimulators with electromyography (EMG) neuromonitoring is comparable to awake placement for achieving paresthesia coverage in chronic pain patients. Determine whether non-awake placement reduces procedure time, risk for revision, risk for complications.
Patient Population:	Patients with successful spinal cord stimulator (SCS) trials presenting for permanent implantation of a paddle electrode in the thoracic region
Population Size:	Approximately 50
Structure:	The study is designed as a prospective, multicenter, parallel design, non-randomized, non-blinded, 6-month study.
Method of Assignment:	All patients who comply with the inclusion/exclusion criteria will be enrolled chronologically.
Randomization:	There will be no randomization of the patients. Patients recruited and enrolled at St. Luke's Neurological Associates or Thomas Jefferson University will undergo implantation under general anesthesia with EMG neuromonitoring for testing of the distribution of induced paresthesia ("non-awake"). Patients recruited and enrolled at Geisinger or Milton S. Hershey Medical Centers will undergo implantation of the device in an awake operation with local anesthetic and patient interaction for testing of the distribution of the induced paresthesia ("awake").
Statistical Analysis:	The primary endpoints will be procedure time, rates of adverse events, specifically lead revisions, and patient satisfaction. An additional endpoint will be the proportion of painful regions covered by paresthesia in non-awake compared to awake patients
Adverse Events	All device/procedure-related and all serious adverse events that occur and are volunteered by the patient and solicited by the site staff will be collected.

1. Introduction

Spinal cord stimulation (SCS) is an adjustable, non-destructive, therapy in which an electrical current is applied to the spinal cord for management of neuropathic pain. Leads are placed in the epidural space, which apply electrical stimulation to the spinal cord. It has been used for many years and has proven to be effective in the treatment of chronic, intractable pain including failed back surgery syndrome CRPS, phantom limb pain, cancer pain, peripheral vascular disease, and ischemic limb pain (Burchiel et al., 1996; Cameron, 2004; Kemler, de Vet, Barendse, van den Wildenberg, & van Kleef, 2008; Khan, Raza, & Khan, 2005; Turner, Loeser, Deyo, & Sanders, 2004).

The success of the therapy relies on the ability to create an overlap between the pain areas and the device-induced paresthesia. Lead placement has historically been done under awake conditions, using direct feedback from the patient in order to define adequate paresthesia coverage. The awake operation is performed while the patient is under local anesthesia, which is very stressful for the patient and predisposes them to movement. This can lead to decreased patient satisfaction, equipment migration, undesired stimulation effects, and treatment failure.

Implantation under general anesthesia using electromyography (EMG) responses to determine paresthesia coverage may offer advantages over the awake procedure. This “non-awake” technique is potentially more comfortable for the patient and may carry less risk for revision. Recently, several retrospective studies have found that the non-awake procedure is safe and at least as efficacious in producing adequate paresthesia coverage as the awake procedure (Air, Toczyl, & Mandybur, 2012; Falowski et al., 2011; Shils & Arle, 2012). Falowski et al. found that the non-awake procedure resulted in the same or fewer revisions as the awake procedure. Shils observed a 30 minutes (33%) reduction in procedure time.

These studies are promising, yet there is a need for a prospective study to determine the equivalency or benefit of the non-awake procedure. The purpose of the proposed clinical study is to collect data necessary to demonstrate the safety and efficacy of non-awake implantation of SCS paddle leads compared to the awake procedure. The study is designed to evaluate whether non-awake placement reduces procedure time, complication rates, and/or revision rates while offering comparable paresthesia coverage as the awake procedure.

2. Objectives/Endpoints

2.1. Primary Objective

To demonstrate the safety and efficacy of a non-awake implantation method (EMG neuromonitoring) of a SCS paddle lead as compared to an awake implantation method (with local anesthesia and patient feedback).

2.2. Secondary Objective

To demonstrate that implantation non-awake and awake methods result in comparable paresthesia coverage of painful regions.

2.3. Primary Variables

- Procedure time
- Number and type of adverse events
- Number of revisions

2.4. Secondary Variables

- Pain mapping and paresthesia coverage

2.5. Additional Data

- Demographics: gender, age, height, weight, ethnicity, marital status
- Pain history: primary diagnosis, pain duration, pain etiology, prior treatments
- Medication usage including rescue medication
- Pain quality as assessed by the Short-Form McGill Pain Questionnaire version 2
- Quality of life as assessed by EuroQol (EQ-5D) generic health index questionnaire
- Patient global impression of satisfaction with device implantation compared to trial system implantation.
- Surgery and device information
- Programming data
- Patient reported perception of pain relief.
- Responder classification for average daily overall pain. Responders are classified as patients with $\geq 30\%$ or $\geq 50\%$ reduction in pain.

3. Study Design

3.1. Design

This is a post-market, prospective, multicenter, parallel designed, non-randomized, non-blinded, 6-month study. A minimum of 50 patients will be implanted from up to 4 active sites, coordinated by a single lead investigator.

Patients who have had a successful SCS trial and are indicated for permanent implantation will be approached to participate in this study prior to permanent implantation. Patients will be recruited and enrolled by physicians at any one of the involved sites. Each Investigator will only use one method (awake or non-awake) according to his/her typical practice. Patients will receive treatment from their enrolling physician.

[figure not shown]

Table 1: Study Schedule

Timing of visit	Activities at visit	Case Report Forms
Screening and Informed Consent (may be immediately after Trial System Explant)	Patient evaluated for eligibility Patient signs informed consent Schedule patient for baseline evaluation at treatment site	Enrollment Form Inclusion/Exclusion Criteria Form
Baseline Evaluation 7-28 days after screening	Patient completes questionnaires Complete history and physical exam Record current medication use Collect patient reported data	Baseline Self Evaluation Form Pain Location Form Pain Evaluation Form SF-MPQ-2 (Pain Quality) EQ-5D (Quality of life) Medication Form
Permanent System Implantation	Permanent system implantation Record any complications Record any changes in medication Discourage activation at discharge Save digital recording or EMG recording if system permits.	Surgery Form Adverse Event Form Programming Form (if programmed at discharge) Medication Form
Initial Programming Visit	Record any complications Record any changes in medication Provide patient with the patient programmer and charging system Record patient's global impression of satisfaction with the implant procedure.	Programming Form Paresthesia Coverage Form Patient Global Impression Form Medication Form
6 weeks 42 ± 7 days after activation	Record any complications Record any changes in medication Patient completes questionnaires Modify programming parameters (if necessary) Collect patient reported data	Follow-up Visit Form Pain Evaluation Form Pain Location Form Programming Form SF-MPQ-2 (Pain Quality) EQ-5D (Quality of life) Paresthesia Coverage Form Medication Form
24 weeks 168 ± 14 days after activation	Record any complications Record any changes in medication Patient completes questionnaires Modify programming parameters (if necessary) Collect patient reported data	Follow-up Visit Form Pain Evaluation Form Pain Location Form Programming Form SF-MPQ-2 (Pain Quality) EQ-5D (Quality of life) Paresthesia Coverage Form Medication Form
Unscheduled Visit (as needed)	Record any unscheduled visit Record any changes in medication Record any other health care utilized Record any complications	Unscheduled Visit Form Medication Form HCOR Form Adverse Event Form

Timing of visit	Activities at visit	Case Report Forms
	Record programming changes Record paresthesia changes	Product Out of Service Form Programming Form Paresthesia Location Form Additional Surgery Form Exit and Withdrawal form

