3.2. Justification for study given risks/benefit outcome

Spinal Cord Stimulation is a commercially available neurostimulation therapy available for treatment of chronic intractable pain of the trunk and/or limbs to patients today. Traditionally, SCS leads are placed in the epidural space while the patient is awake and able to give direct feedback in order to ensure adequate paresthesia coverage. Using EMG for lead implantation will allow the patient to be placed under general anesthesia and to be potentially more comfortable than during the awake procedure. The purpose of the proposed clinical study is to collect data necessary to make a direct comparison between the awake procedure and the non-awake procedure using EMG.

The Investigator will review the subject's medical record to ensure that the subject complies with all inclusion/exclusion criteria. The target population consists of subjects indicated for a neurostimulation system. The present study will permit the physician to adhere to their standard of care for continued medication usage or any current treatment methods prior to enrollment.

The risks and benefits are the same for these two lead placement techniques since the implant procedure is the same. No additional adverse events from non-awake placement are anticipated. Considering the severity of chronic pain and its debilitating effect on patients' lives, spinal cord stimulation provides an alternative means of pain reduction with minimal risk for subjects who have exhausted other options.

4. Study Devices

All study devices are in commercial distribution in the United States and Europe as an aid in the management of chronic intractable pain of the trunk and/or limbs. St. Jude Medical (SJM) received FDA approval for the Eon Mini IPG system under the PMA P010032/S32 and Eon IPG system under the PMA P010032/S014. The Lamitrode leads received clearance under K990469 (standard), K053250 (90 and 110cm), K033429 (C-Series), K022222 (S-Series), K063080 (Tripole 8C, 16C, and Exclaim), K090907 (Penta) and K991784 (extensions).

Any SJM market-cleared IPG may be used. Any SJM market-cleared paddle lead may be used. Percutaneous leads may not be used.

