5.2. Exclusion Criteria

A patient will be excluded from participation in this study if they meet any one of the following criteria:

1. Patient currently participating in a clinical investigation that includes an active treatment arm.
2. Patient has an infusion pump or any implantable neurostimulation device
3. Patient has an existing medical condition that is likely to require repetitive MRI evaluation in the future (i.e. epilepsy, stroke, multiple sclerosis, acoustic neuroma, tumor)
4. Patient has an existing medical condition that is likely to require the use of diathermy in the future
5. Patient is immunocompromised
6. Patient has documented history of allergic response to titanium or silicone
7. Patient has a documented history of substance abuse (narcotics, alcohol, etc.) or substance dependency in the 6 months prior to baseline data collection
8. Female candidates of child bearing potential that are pregnant (confirmed by positive pregnancy test)

6. Patient Assignment to Procedure

Each patient who is willing to participate in the study, signs the informed consent, and complies with the inclusion/exclusion criteria will be enrolled in the study. Patients are considered enrolled in the study from the moment the patient has provided written informed consent. Each patient is enrolled chronologically on a patient enrollment log and given a patient number for the duration of the study.

Patients will be enrolled in a 1:1 fashion to the method of surgical implantation, either awake or non-awake. Patients will be treated by the enrolling physician. Patients recruited and enrolled at St. Luke's Neurological Associates or Thomas Jefferson University will undergo implantation under general anesthesia with EMG neuromonitoring for testing of the distribution of induced paresthesia ("non-awake"). Patients recruited and enrolled at Geisinger or Milton S. Hershey Medical Centers will undergo implantation of the device in an awake operation with local anesthetic and patient interaction for testing of the distribution of the induced paresthesia ("awake"). Each treatment arm will enroll a maximum of 30 patients. No blinding is necessary for the purposes of assigned study arm.

7. Methods and Procedures

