10.3. Primary Analysis

10.3.1. Procedure Time

Hypothesis:

The non-awake method is faster than the awake method.

Metrics:

Skin-to-skin surgical time
Intraoperative programming time
Total fluoroscopy used (time and dose)

Statistical Tests:

Test for normality (such as Jarque-Bera)
Unpaired, two-sided Student's t-tests (normally distributed continuous data) or Mann-Whitney rank sums test (skewed continuous data)
Significance at $\alpha < 0.05$, with no adjustment for the multiple comparisons

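### Method is fully nested in site and surgeon without randomisation, yet the claim that non-awake placement is faster rests on an unadjusted two-group test, with no pre-specified case-mix-adjusted or by-site result

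*Combined protocol and SAP*

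**What the plan says.** The Protocol Summary states that "There will be no randomization of the patients". It names two sites that will do only non-awake implants and two others that will do only awake implants, and section 6 repeats this. Section 3.1 adds that "Each Investigator will only use one method (awake or non-awake) according to his/her typical practice", and section 6 that "Patients will be treated by the enrolling physician". The 1:1 enrolment in section 6 fixes the numbers per arm; it does not put both methods into any one site.

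Under section 7.6 the surgical approach, anaesthesia and monitoring follow each centre's custom, with implantation left to the investigator's discretion.

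The hypothesis in section 10.3.1 is "The non-awake method is faster than the awake method". The metrics are skin-to-skin time, programming time, and fluoroscopy time and dose, unranked. Each is compared by an unpaired two-sided t-test, or a Mann-Whitney test if skewed. No covariate, stratum or by-site summary is named there or in sections 10.3.2 to 10.4.1.

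Section 2.5 lists age, height, weight, diagnosis and other pain history as collected, and section 7.4 adds a baseline Pain Location Form. Section 10.5 gives the additional data summary statistics and allows post-hoc work.

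The aims are worded about the method. The Introduction says that "there is a need for a prospective study to determine the equivalency or benefit of the non-awake procedure", and section 3.2 says that the data are to "make a direct comparison between the awake procedure and the non-awake procedure using EMG".

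**The concern.** An unadjusted difference between the arms mixes three things: the method, the sites and surgeons who use it, and the patients those sites enrol. Nothing in the design balances the last two.

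The patient component can be partly handled in the analysis, because relevant baseline data are already collected. As written, the plan leaves any such analysis to post-hoc choice, which is weaker evidence than a model fixed in advance. If the non-awake sites happen to enrol easier cases, the planned test can find a time saving that is not there; if they enrol harder cases, it can miss a real one.

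The site and surgeon component cannot be removed by any analysis of these data, because a site term and a method term are aliased. It can only be stated, and the plan does not say that the measured contrast is method plus site and surgeon.

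**Working it through.** **Inputs from the documents.** Minimum 50 patients, 1:1, so 25 per arm; 5% level; planning times of 60 and 90 minutes, a difference of 30 (section 10.2, Table 2). Two-sided test (section 10.3.1).

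**Inputs that the documents do not give.** The SD of procedure time, the power, the size of any imbalance and the strength of any covariate. These are assumptions below, shown as ranges.

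**The plan's own figure.** N = 50 is said to come from simulations and cannot be reproduced without an SD and a power. Working backwards from the time row with SD = 30 / (z0.975 + z_power) × √(25/2):
- 80% power: 30 / (1.960 + 0.842) × 3.536 = 37.9 min
- 90% power: 30 / (1.960 + 1.282) × 3.536 = 32.7 min

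I therefore use SD 25, 30 and 37.9.

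**Size of the bias.** Bias in SD units = imbalance × covariate coefficient. An imbalance of 0.25 to 0.5 SD with a coefficient of 0.3 to 0.5 gives 0.25 × 0.3 = 0.075 to 0.5 × 0.5 = 0.25 SD. In minutes this is 1.9-6.3 at SD 25, 2.3-7.5 at SD 30 and 2.8-9.5 at SD 37.9.

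**Probability of concluding that non-awake is faster.** This is P(T > 2.011), where T is noncentral t with 48 df and noncentrality (30/SD or 0, plus or minus the bias) × √12.5, and √12.5 = 3.536.

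No true difference (nominal 2.5% in this direction):

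| Cases at non-awake sites | Bias 0.075 SD | Bias 0.25 SD |
|---|---|---|
| Easier (noncentrality +0.265, +0.884) | 4.5% | 13.7% |
| Harder (noncentrality -0.265, -0.884) | 1.3% | 0.2% |

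True difference of 30 minutes, harder cases at the non-awake sites:

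| SD | 30/SD | No bias | Bias 0.075 SD | Bias 0.25 SD |
|---|---|---|---|---|
| 25 | 1.20 | 99% | 97% | 91% |
| 30 | 1.00 | 93% | 89% | 74% |
| 37.9 | 0.79 | 78% | 70% | 47% |

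**What adjustment recovers.** In simulation at SD 30, with the confounder and four unrelated columns in the model, the false rate returned to 2.4-2.6% and power to 92-96%. This is a best case: the confounder is in the model and measured without error.

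**What adjustment costs if the covariates predict nothing.** Age, BMI, three diagnosis levels (two columns) and number of painful regions make five columns, leaving 50 - 2 - 5 = 43 df. The unadjusted half-width is 2.011 × SD × √(2/25), or 17.1 min at SD 30; five columns widen it by about 6%, to about 18 min. With two diagnosis levels (four columns) it widens by about 5%. With five columns, power for 30 minutes falls by about 1 point at SD 25, 3 at SD 30 and 4 to 5 at SD 37.9.

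**Revisions.** Table 2 implies 25 × (0.15 + 0.30) = 11.25 revisions. If lead repositionings also count, add 25 × (0.01 + 0.15) = 4, giving about 15. Table 2 gives no overall adverse-event rate.

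All of this uses the t-test branch; the Mann-Whitney branch was not calculated.

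**The case against.** The plan does not hide the link between site and method: it is openly non-randomised and names which sites use which method. That stands. For the nesting itself the remedy is only a sentence of interpretation, and the analysis gap is confined to measured case mix.

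The case-mix sizes are hypothetical. The documents show no imbalance, give no evidence that these covariates predict surgical time, and apply the same eligibility criteria at all sites. This also stands. It limits what can be said about size and direction, but not the point that an exposed comparison has no pre-specified handling.

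A reader might infer that clustering by site makes the planned p-value badly wrong. If the four sites are treated as a random sample, the t-test falsely rejects about 12%, 19% and 30% of the time at an assumed ICC of 0.05, 0.10 and 0.20. The documents give no ICC and do not present the sites as a sample of a wider population. With fixed site differences of the same spread and equal arm means, the rates are 4.4%, 4.1% and 2.7%, so there is no inflation. The supportable point is narrower: patient-level p-values exclude between-site variation, and the plan should say so.

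A reader might also infer that adjustment would isolate the effect of the method, or that the design favours the non-awake arm. Neither follows. Adjustment reaches measured patient differences only, and the bias could run either way.

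**Conclusion.** The concern holds in this form. Method cannot be separated from site and surgeon, the time claim rests on an unadjusted test, and baseline data already collected are not used to protect it. Following the plan exactly could give a case-mix-biased conclusion about speed in either direction, and any conclusion would describe method plus site and surgeon.

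The nesting and the missing pre-specification are matters of text and need no assumption. The magnitudes rest on assumed SDs, imbalances and coefficients and on normally distributed times. They show that moderate imbalance matters at 25 per arm, not that it will occur. This is a cheap improvement to the plan; it does not make the trial unworkable.

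**What to change.** In section 10.3.1, keep the planned test. Beside it, pre-specify for each listed procedure-time metric, without ranking them, a regression (log scale if skewed) on method plus a short list fixed before any data are seen by arm: age, BMI from height and weight, primary diagnosis in at most three levels, and number of painful regions on the baseline Pain Location Form. Use the same model as a sensitivity analysis for paresthesia coverage in section 10.4.1.

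Keep chi-square or Fisher's exact test for revisions and adverse events. Some 11 to 15 revisions are too few for this model, and the documents give no basis for planning one for adverse events.

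Report every primary outcome by site. State that the contrast is method plus site and surgeon, that adjustment covers measured case mix only, and that patient-level p-values exclude between-site variation. A formal site-level interval is not worth adding: with two sites per arm it has 2 df and would be too wide to inform a decision.

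The cost is SAP wording and modest programming, with no new data, plus the small loss of precision shown above if the covariates predict nothing. The conclusion becomes more cautious.
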